5.3 Dose Selection and Administration

Two doses of *hMaxi-K* will be evaluated: 16000 µg and 24000 µg.

Up to 9 female participants (6 participants on active treatment and 3 on placebo) will be enrolled per dose level "arm". The 2 active doses to be evaluated sequentially are 16000µg and 24000µg compared to direct intramuscular injection into the bladder wall of PBS-20% sucrose (control group). Additional participants may be enrolled for evaluating the tolerability to a given dose.

Each arm of 9 participants per dose level will be enrolled sequentially, beginning with the lowest dose. Enrollment of the first 4 participants in each cohort will be managed directly by the sponsor (or their designee) with a 2-day waiting period following each participants dosing. The next participant will be enrolled only after the site has contacted the previously dosed participant on day 3 following transfer to determine if a clinically significant adverse event occurred. The site will contact the clinical monitor with the result of that contact. In the event that no event occurred the next participant will be enrolled. The DSMB will review eligibility and all available safety data after the 5th participant has been administered study drug in the first dosing cohort. This first review will occur as soon as possible after the 5th participant's 3-Day Post-visit 2 telephone contact. Following their review of the safety data, the DSMB will recommend whether enrollment into the first dosing cohort may proceed. This process will be repeated through the 5th participant in each cohort before the balance of the cohort (4 additional participants) is enrolled.

If a clinically serious sign or symptom is reported the medical monitor will contact all the sites and no further enrollment will be done until the medical monitor or sponsor gives permission. In addition, enrollment into the next cohort or arm in the series (at the next highest dose) will be dependent on safety dose-limiting toxicity assessments as per Section 5.2 There has been no toxicity observed at any dose level in any of the preclinical or clinical trials at any dose to date, including multiple dosing in the ED rat model. In the completed clinical study evaluating intracorporal administration of up to 16000 µg *hMaxi-K* in participants with ED, there was only one adverse event considered possibly related to *hMaxi-K* (“tingling warmth in the glans”).

In the previous OAB trial there were several events considered possibly related: UTI; AV block Mobitz type II (possibly related; mild severity, 170 days post treatment); fatigue, headache, shaking chills, and insomnia (all possibly related; mild-moderate severity; 13-76 days post treatment). In the placebo group heart palpitations were reported (possibly related, mild severity, occurred 6 days post treatment).

The obstructed bladder pre-clinical studies in the rat evaluated single doses of up to 1000 µg based on surface area of the bladder. In the rat ED model, doses of up to 1000 µg were administered by intracavernous injection. In men with ED, doses of up to 16000 µg were administered by injection into the corpus cavernosum (similar to iv). For ease of administration (based upon manufacture and storage of the *hMaxi-K*), during this OAB trial 16,000 and 24,000 µg of *hMaxi-K* have been chosen for bladder wall injection. These concentrations of drug are well within the doses used in the preclinical studies. The doses evaluated in this trial will be equivalent to 240 and 480 µg used in the rat studies.

In addition to preclinical toxicology data, selection of dose was also based upon activity seen in the preclinical pharmacology studies. In the Partial Urethral Obstruction (PUO) studies in female rats, 100 µg in one ml bladder instillation demonstrated highly significant changes. The 100µg dose also corrects detrusor overactivity in the male PUO model. Therefore, based upon preclinical results one would expect to observe an effect in the lowest dose. A rabbit study to evaluate the distribution of different volumes of gene transfer injected into the bladder wall was performed prior to initiation of the clinical trial using direct intravesicular injections in women with OAB. Nine female Adult New Zealand white rabbits weighing an average of 6 pounds were used. The animals were anesthetized and pVAX-*lacZ* was to be injected into the detrusor in 0.05, 0.1, and 0.15 ml aliquots into 4, 8, and 10 sites in the bladder wall. An additional set of 3 animals was to be injected with carrier alone at only the highest volume of carrier (4, 8, or 10 sites x 0.15

ml). The plasmids were in solution at a concentration of 4000 microgr/ml. One week later the animals were euthanized and the bladders excised and weighed. Areas with blue color were prepared for histological examination and molecular analysis. Molecular analysis of *hslo* expression tissue was done with RNA extraction and real time PCR.

One rabbit was given the 0.05 ml injection. Six rabbits had 0.1 ml at 4, 8, and 10 sites (3 from inside the bladder; 3 from outside the bladder). Three rabbits had 0.15 ml at 4, 8, and 10 sites. Results indicated that those rabbits with a greater number of injections (8-10 injections) had less expression than some animals with the smallest number of injections (4 injections). The overall conclusion is that the direct injection into the bladder wall results in expression of the gene however, it seems to work best with wider dispersion of the injections perhaps 1 cm apart.

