Up to 9 female participants (6 participants on active treatment and 3 on placebo) will be enrolled per dose level “arm”. The 2 active doses to be evaluated sequentially are 16000 µg and 24000µg compared to intramuscular injections into the bladder wall of PBS-20% sucrose (control group). Additional participants may be enrolled for evaluating the tolerability to a given dose. Each arm of 9 participants per dose level will be enrolled sequentially, beginning with the lowest dose. Enrollment of the first 5 participants in each cohort will be managed directly by the sponsor (or their designee) with a 2-day waiting period following each participants dosing. The next participant will be enrolled only after the site has contacted the previously dosed participant on day 3 following transfer to determine if a clinically significant adverse event occurred. The site will contact the clinical monitor with the result of that contact. In the event that no event occurred the next participant will be enrolled. The DSMB will review eligibility and all available safety data after the 5th participant has been administered study drug in the first dosing cohort. This first review will occur as soon as possible after the 5th participant’s 3-Day Post-visit 2 telephone contact. Following their review of the safety data, the DSMB will recommend whether enrollment into the first dosing cohort may proceed. This process will be repeated through the 5th participant in each cohort before the balance of the cohort (4 additional participants) is enrolled. If a clinically serious sign or symptom is reported the medical monitor will contact all the sites and no further enrollment will be done until the medical monitor or sponsor gives permission. In addition, enrollment into the next cohort or arm in the series (at the next highest dose) will be dependent on safety dose-limiting toxicity assessments as per Section 5.2.

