5.2.1 Stopping Rules

No acute toxicity was seen in the preclinical studies in rats with administered intravenous doses up to 1000 µg (approximately 1500 µg/kg in the rat). Potential toxicities would be those that could occur (1) because of enhanced efflux of K^+ with resultant decreased intracellular Ca^{++} concentration, thus altering smooth muscle function in diverse organ systems; (2) reaction to the naked DNA.

In the event that any participant experiences one of the following events, **no** additional participants will be accrued and **no** further doses of hMaxi-K will be administered until the DSMB and FDA have reviewed the case and have provided their recommendation to the sponsor.

- 1) Urinary retention, i.e., the inability to micturate for more than 12 hours with a urine bladder volume (greater than 400 ml established by bladder scan) that requires placement of a bladder drainage catheter.
- 2) Any adverse event of Grade 2 that last longer than 96 hours or Grade 3 or higher in the blood chemistry, completed blood count or urine categories of adverse event criteria listed in Appendix A.
- 3) In the event of a clinically significant sign or symptom reported by the site PI to the medical monitor in any of the first four participants of each cohort unless permission is given by the medical monitor.
- 4) Bladder pain and /or irritation that persists for four hours or more after gene transfer that is thought by the Principal Investigator not to be related to acute trauma from the cystoscopy, direct bladder muscle injections, and catheterization.

Clinical data regarding the event will be collected, reviewed, and discussed with DSMB and FDA. After review of these data with FDA the clinical study may resume **only** with concurrence of FDA.

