11.3 Data Safety Monitoring Board (DSMB)

In order to monitor the safety of participants participating in this study, the sponsor will establish an independent Data Safety Monitoring Board (DSMB). The members will have training in medicine and/or gene therapy. All members will be independent of the study conduct.

The DSMB will review eligibility and all available safety data after the 5th participant has been administered study drug in the first dosing cohort. This first review will occur as soon as possible after the 5th participant's 3-Day Post-visit 2 telephone contact. Following their review of the

safety data, the DSMB will recommend whether enrollment into the first dosing cohort may proceed.

The DSMB will review participant's eligibility data and all safety data at 4 weeks following administration of study drug for the last participant enrolled into each dose cohort, in order to assess the need for modifications in safety monitoring and/or dosing. Following their review of the safety data for the last participant in the cohort at the 4th week post-dosing, the DSMB will recommend whether or not enrollment into the next dosing cohort may proceed (Section 5.2). The DSMB will also review the clinical safety data from the participants in all the dosing cohorts at the six month timepoint following the final dose.

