4. STUDY DESIGN

4.1. General Study Design and Plan

This study is a double blind, placebo-controlled, multicenter, sequential active dose, Phase 1 study in females with moderate OAB/DO of \geq six months duration.

Up to 9 female participants (6 participants on active treatment and 3 on placebo) will be enrolled per dose level “arm”. The 2 active doses to be evaluated sequentially are 16,000 μg and 24,000 μg compared to intramuscular injections into the bladder wall of PBS-20% sucrose (control group). Additional participants may be enrolled for evaluating the tolerability to a given dose. Each arm of 9 participants per dose level will be enrolled sequentially, beginning with the lowest dose. Enrollment of the first 5 participants in each cohort will be managed directly by the sponsor (or their designee) with a 2 day waiting period following each participants dosing. The next participant will be enrolled only after the site has contacted the previously dosed participant on Day 3 following gene transfer to determine if a clinically significant adverse event occurred. The site will provide the clinical monitor with the result of that contact. In the event that no event occurred the next participant will be enrolled. The Data Safety Monitoring Board (DSMB) will review eligibility and all available safety data after the 5th participant has been administered study drug in the first dosing cohort. This first review will occur as soon as possible after the 5th participant’s 3 day post-visit 2 telephone contact. Following their review of the safety data, the DSMB will recommend whether enrollment into the first dosing cohort may proceed. This process will be repeated through the 5th participant in each cohort before the balance of the cohort (4 additional participants) is enrolled. If a clinically serious sign or symptom is reported the medical monitor will contact all sites and no further enrollment will be done until the Medical Monitor or Sponsor gives permission. In addition, enrollment into the next cohort or arm in the series (at the next highest dose) will be dependent on safety dose-limiting toxicity assessments as per Protocol Section 5.2.

Protocol [Table 1](#) shows the detailed event schedules of the study.

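### Protocol 5.3 puts the first 4 participants of each cohort under direct sponsor management but Protocol 3.1 and SAP 4.1 say 5; one number must change, and the reach of stopping rule 3 should be settled with it

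*Protocol*

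**What the plan says.** Three sections describe the staggered start of each dose cohort in almost identical paragraphs. They differ in one number.

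- Protocol 5.3, Dose Selection and Administration: "Enrollment of the first 4 participants in each cohort will be managed directly by the sponsor".
- Protocol 3.1, Study Design: "Enrollment of the first 5 participants in each cohort will be managed directly by the sponsor". SAP 4.1 has the same sentence, also with 5.

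All three then place a DSMB review after the 5th participant. Protocol 5.3 continues: "This process will be repeated through the 5th participant in each cohort before the balance of the cohort (4 additional participants) is enrolled". SAP 4.1 likewise has the review "before the balance of the cohort (4 additional participants) is enrolled". Protocol 11.3 confirms the review point for the first cohort: "The DSMB will review eligibility and all available safety data after the 5th participant has been administered study drug in the first dosing cohort".

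Protocol 5.2.1 lists four events that stop accrual and dosing until the DSMB and FDA have reviewed the case. The lead-in is general: "In the event that any participant experiences one of the following events". Rule 3, on a clinically significant sign or symptom, is narrower. It applies only "in any of the first four participants of each cohort unless permission is given by the medical monitor".

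Separately, Protocol 3.1 and 5.3 provide a general pause for a clinically serious sign or symptom, under which "no further enrollment will be done until the medical monitor or sponsor gives permission".

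**The concern.** These are the early-dosing safety rules of a phase 1 gene-transfer trial whose primary objective is safety. The protocol allows up to six sites, and the sites and monitors have two different numbers for who is under direct sponsor management. The 5th participant of each cohort is inside that group in Protocol 3.1 and SAP 4.1 and outside it in Protocol 5.3.

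Rule 3 raises a related question. It has no time limit, so a clinically significant sign in participant 4 that is reported weeks after dosing still triggers a DSMB-and-FDA hold, unless the medical monitor gives permission. It also triggers the event-driven DSMB review in Protocol 5.2.2. The same sign in participant 5 triggers neither unless it meets rule 1, 2 or 4, although she is dosed before the DSMB gate just as participants 1 to 4 are.

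**Working it through.** **Inputs.** Cohort size 9, with two cohorts, so 18 participants (Protocol 3.1 and Synopsis). DSMB gate after the 5th participant, leaving 4 (Protocol 3.1 and 5.3, SAP 4.1). Rule 3 covers the first four (Protocol 5.2.1). Next scheduled DSMB review is 4 weeks after the last participant of the cohort is dosed (Protocol 5.2.2). No replacements or added participants are assumed.

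**Step 1: the sections side by side.**

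| Place | Sponsor-managed group | DSMB gate | Balance |
|---|---|---|---|
| Protocol 3.1 | first 5 | after 5th | 4 |
| Protocol 5.3 | first 4 | after 5th | 4 |
| SAP 4.1 | first 5 | after 5th | 4 |
| Protocol 5.2.1, rule 3 | (rule covers first four) | – | – |

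**Step 2: the plan's own count.** Balance = cohort size − participants dosed before the gate = 9 − 5 = 4, which reproduces the stated balance. This confirms the position of the gate. It says nothing directly about the sponsor-managed group, because no section defines the balance as what is left after that group.

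**Step 3: does the number change any dosing interval?** With 4, the wait and day-3 contact follow participants 1 to 4, participant 5 is dosed, and the DSMB reviews after her day-3 call. With 5, the wait also follows participant 5, but participant 6 must in any case await the DSMB review after that same call. The intervals are identical.

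**Step 4: reach of rule 3.**
- As written: 2 × 4 = 8 of 18 = 44%.
- Extended to five: 2 × 5 = 10 of 18 = 56%.
- Difference: 10 − 8 = 2 of 18 = 11%, the 5th participant of each cohort.

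**Step 5: what the difference amounts to.** A sign in participant 5 that is known by her day-3 call reaches the DSMB at the gate. For one reported later, the 4 remaining participants of the cohort can be dosed before the next scheduled review. That review comes at least 4 weeks after the gate, because participant 9 is dosed after the gate and the review is 4 weeks after her dosing. Late reports are plausible. In the previous overactive-bladder trial, the possibly related events with a stated time came at 6 days (placebo), and at 13 to 76 days and 170 days (active), according to Protocol 5.3. That trial used bladder instillation at lower doses, so this bears on timing and gives no rate.

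**The case against.** A reader might infer from 9 − 5 = 4 that 5 is proven to be the intended number and that Protocol 5.3 is simply a misprint. The documents do not support that. The count fixes the gate only. Protocol 5.3 is coherent as printed: a wait after each of participants 1 to 4, then participant 5, then the DSMB. Rule 3 also says four, so two places in Section 5 agree. SAP 4.1 repeats the Protocol 3.1 paragraph nearly word for word and adds little independent support for 5. A deliberate design is possible, in which rule 3 guards the steps between participants 1 to 5 and the DSMB gate guards the step after participant 5.

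A reader might also infer that participant 5 is left unprotected. She is not. Rules 1, 2 and 4 cover every participant, the general pause covers any clinically serious sign, and the DSMB may ask for extra meetings. The medical monitor can waive rule 3 even for participants 1 to 4.

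These objections stand as limits on the point. They do not remove the contradiction: if four is deliberate, Protocol 3.1 and SAP 4.1 are wrong. Nor do the other safeguards fully replace rule 3. The general pause needs a clinically serious sign, and the medical monitor or sponsor can lift it without DSMB or FDA review.

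**Conclusion.** The contradiction between Protocol 5.3 and Protocol 3.1 with SAP 4.1 is certain and in current text, so one number must change. Five is the better choice because it matches the group dosed before the gate, though it is not proven to be the number intended. No dosing interval depends on it.

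For rule 3, extension to five is a sensible improvement held with moderate confidence; the present four may be deliberate. The gap is narrow. It needs a sign that is clinically significant but not clinically serious, falls outside rules 1, 2 and 4, arises in the 5th participant (2 of 18), and is reported after the gate. In that case no rule 3 hold follows, and up to 4 further participants in that cohort could be dosed before the next scheduled DSMB review. The documents give no event rate, so the number of missed holds cannot be estimated.

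Overall the point is minor, but worth settling because it concerns early-dosing safety rules.

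**What to change.** In Protocol 5.3 (Dose Selection and Administration), change the sponsor-managed group from the first 4 to the first 5. In Protocol 5.2.1, rule 3, change four to five and keep the medical monitor's power to waive. Protocol 3.1 and SAP 4.1 then need no change.

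If the sponsor confirms that four is intended, it should say so explicitly and correct Protocol 3.1 and SAP 4.1 to 4, leaving rule 3 as it is.

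The preferred fix costs two word changes in a protocol amendment. Its downside is that one more participant per cohort, 2 of 18 in all, could trigger a rule 3 pause, which the medical monitor can waive.

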6.6 Laboratory Safety Tests

Laboratory safety tests will be performed at Screening (V1), Baseline (V2) and 1 (V3), 2 (V4), 4 (V5), 12 (V7), and 24 (V8) weeks post dosing with study drug.

The laboratory safety tests include:

- Hematology: V1, V2-V5, V7-V8; Complete blood count (CBC) with differential, platelet count, sedimentation rate (sed. rate), PT and PTT (no PT and PTT at V2 and V4).
- Fasting chemistry: V1, V3-V5, V7-V8; Blood Urea Nitrogen (BUN), creatinine, electrolytes (Na⁺, K⁺, Mg⁺⁺, Ca⁺⁺, CO₂, Cl), albumin, alkaline phosphatase, ALT, AST, GGT, LDH, CPK, total bilirubin, total protein, C-reactive protein (CRP), antinuclear antibody (ANA), and glucose. V4 chemistry testing: Blood Urea Nitrogen (BUN), creatinine, electrolytes (Na⁺, K⁺), C-reactive protein (CRP), glucose, and ANA only.
- At screening, participants of child bearing years must have a serum pregnancy test for beta- HCG if they have not had a hysterectomy. In addition, they must have either a serum FSH >40 IU/L or a history of no menses for more than 12 months to confirm post-menopausal status if a hysterectomy or bilateral tubal ligation has not been done.
- At screening only, participants must have a serum hemoglobin A1c performed

- Urine analysis; Conducted at V1, V1A (by dipstick), V2 (by dipstick), V3-V5, V7-V8; microscopic RBC and WBC, protein, glucose, nitrites, pH, and specific gravity. Dipstick will measure blood, leukocyte esterase and nitrites.
- Urine culture: At Screening Visit 1 and 1A (collect by catheterization) and at V3. At Visit 1A, Visit 5 and Visit 8, prior to cystometry (collect using urodynamic catheter) and repeated with clean void prior to discharge. At Visit 2, collect using urodynamic catheter prior to cystoscopy and first clean voided urine after study drug dosing. If V1A cystometry performed at V1 then urine cultures pre-and post-cystometry should be done using urodynamic catheter before cystometry and repeated with clean void prior to discharge.

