- The time of voiding following drug administration will be recorded. The participant will be observed in the clinic for two hours after the bladder injections are completed. During that time blood pressure and pulse will be measured and recorded by the nurse every 15 minutes. The participant will be asked if there is any persistent pain/irritation in the bladder/urethra and will be treated symptomatically, if needed. The participant will be asked if they have experienced any new symptoms or problems they want to report to the investigator or study personnel. Emergency equipment for resuscitation will be immediately available in the event of an unexpected serious reaction to the study drug;
- Participants are required to stay at the study site for at least 2 to 3 hours after dosing. They may be asked stay longer if the investigator believes it is necessary.

- Collect first voided urine (clean void) after drug administration for culture prior to discharge;
- Provide participant with diary materials;
- Provide participant with prophylactic antibiotics prior to discharge (to take immediately and for the 2 days following Visit 2)
- Instruct the participant to complete daily voiding diaries for 7 days prior to next visit and return with results at next visit, including pads used for 72 hours prior to that visit (and clean pad to be used as baseline).

7.5 1-Day and 3-Day Post Visit 2 Telephone Contact

One day and three days (3 days \pm 1 day) following Visit 2 (when the participant received the bladder injections) she should be contacted to assess for any problems she may be experiencing. The patient must be asked in a general fashion if she has had any complaints since her last visit. All adverse events should be documented on the adverse event E-CRF. The patient may be brought back to the clinic sooner than Visit 3 if required.

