7.6 Visit 3 (Study Week 1 +2 days)

The following tests and evaluations will be performed:

- Review medical history for events since last visit;
- Review concomitant meds since last visit;
- Review voiding diaries;
- Participants complete global assessment of disease state and response to treatment;
- Physical examination including urogenital examination and vital signs
- Electrocardiogram;
- Obtain blood for the following laboratory determinations:
 - Hematology: Complete Blood Count (CBC) with differential, platelet count, sedimentation rate (sed rate), PT and PTT.
 - Fasting chemistry: Blood Urea Nitrogen (BUN), creatinine, electrolytes (Na⁺, K⁺, Ca⁺⁺, Mg⁺⁺, CO₂, Cl), albumin, alkaline phosphatase, ALT, AST, GGT, LDH, CPK, total bilirubin, total protein, C-reactive protein (CRP), antinuclear antibody (ANA), and glucose;
- Obtain urine for routine urine analysis: microscopic RBC and WBC, protein, glucose, nitrites, and specific gravity, pH;
- Collect and weigh pads used for 72 hours;
- Obtain urine and blood specimen for analysis of *hSlo* cDNA with PCR;
- Obtain urine culture by clean void;

- Provide patient with diary materials;
- Instruct the participant to complete daily voiding diaries for 7 days prior to next visit and return with results at next visit including pads used for 72 hours prior to that visit (and clean pad to be used as a baseline). The site must call participants at least 7-8 days prior to next scheduled visit to remind patient to complete the diaries for 7 days prior to next visit;

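### The DSMB review that releases the last four of each cohort can be held before the 5th participant has any post-dose safety laboratory results

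*Protocol*

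**What the plan says.** Protocol 3.1, 5.3 (Dose Selection and Administration) and 11.3, and SAP 4.1, schedule a DSMB review at the earliest opportunity after the 5th participant's "3-Day Post-visit 2 telephone contact. Following their review of the safety data, the DSMB will recommend" whether enrolment continues. The board looks at whatever safety data exist by then; no minimum content is set. Sections 3.1 and 5.3 and SAP 4.1 apply this to both cohorts: "This process will be repeated through the 5th participant in each cohort before the balance of the cohort (4 additional participants) is enrolled".

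For the laboratory schedule, protocol 6.6 states: "Laboratory safety tests will be performed at Screening (V1), Baseline (V2) and 1 (V3), 2 (V4), 4 (V5"), with later visits following. Table 1 puts Visit 3 at Day 8 with a window of +2 days. Visit 2 hematology is drawn before dosing, and Visit 2 has no chemistry (7.4). After dosing on Day 0 the participant has two hours of blood pressure and pulse, an ECG at 2 hours, a urine culture, hSlo samples, a recorded time of voiding and questions about pain and new symptoms. She is then telephoned on Days 1 and 3. On those calls, "The patient must be asked in a general fashion if she has had any complaints since her last visit" (7.5), and she may be recalled before Visit 3 if needed.

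Stopping rule 2 in 5.2.1 covers "Any adverse event of Grade 2 that last longer than 96 hours or Grade 3 or higher in the blood chemistry, completed blood count"; it extends to urinary findings as well.

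**The concern.** The review exists so that an independent board can look before four more women are exposed. As timed, it can take place when the newest participant has been followed for three days and has no post-dose blood count, chemistry or urinalysis. The protocol's own anticipated toxicities (5.2.1) are altered potassium and calcium handling in smooth muscle and a reaction to naked DNA. The Visit 3 panel includes electrolytes, blood count, CRP and ANA, which bear on both.

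Once the gate opens, no spacing is stated for participants 6 to 9, so some or all could be dosed before those results arrive. This matters most in cohort 2. The 24,000 µg dose is above every earlier human dose the protocol describes (up to 16,000 µg by injection in the erectile dysfunction study and 10,000 µg by instillation in the earlier OAB study). Cohort 1 data at 16,000 µg cannot speak to it directly.

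**Working it through.** The plan gives no figure of its own to reproduce; this is timeline arithmetic plus one illustrative probability.

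**Inputs.** From the protocol: the next participant is enrolled only after the previous one's Day-3 contact (3.1, 5.3); the contact window is ±1 day (Table 1); Visit 3 is on Day 8 to 10 (Table 1); each cohort has 6 active and 3 placebo (5.3.1). Assumed, not in the documents: block size, and the risk r of a drug-caused laboratory abnormality visible by Visit 3.

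**Follow-up at the trigger.**
- The 5th participant is at Day 3, or 72 hours. Visit 3 is 8 − 3 = 5 to 10 − 3 = 7 days away. Rule 2's Grade 2 limb needs more than 96 hours; even a Day-4 call only reaches 4 × 24 = 96.
- Dosing every 3 days: doses on days 0, 3, 6, 9 and 12, trigger on day 15, follow-up 15, 12, 9, 6 and 3 days. Three of five have reached Day 8, and two have passed Day 10.
- Dosing every 5 days: doses on days 0, 5, 10, 15 and 20, trigger on day 23, follow-up 23, 18, 13, 8 and 3 days. Four of five have reached Day 8. At 7-day spacing the 4th is at Day 10, the end of the window.
- If calls fell at the early edge of the window (Day 2), only two of five would have reached Day 8.

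**Who is released.** Expected active among the first five is 5 × 6/9 = 3.33, leaving 6 − 3.33 = 2.67 active among the last four.

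**Chance that the review sees at least one case.** With a active participants who have Visit 3 data, the chance is Σ p(a) × [1 − (1 − r)^a]. I took p(a) from one block of 9 (first value) and from 2:1 blocks of 3 (second value). In a block of 9:
- first three: a = 0, 1, 2, 3 with 1, 18, 45, 20 out of 84
- first four: a = 1, 2, 3, 4 with 6, 45, 60, 15 out of 126
- first five: a = 2, 3, 4, 5 with 15, 60, 45, 6 out of 126

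With blocks of 3, the first three contain exactly 2 active, the first four contain 2 (1/3) or 3 (2/3), and the first five contain 3 (2/3) or 4 (1/3).

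Example, first three, block of 9, r = 0.3: (18 × 0.300 + 45 × 0.510 + 20 × 0.657)/84 = 41.49/84 = 0.494.

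| Participants with Visit 3 labs | Mean active | r = 0.1 | r = 0.2 | r = 0.3 | r = 0.4 |
|---|---|---|---|---|---|
| 3 (3-day spacing) | 2.00 | 0.188 / 0.190 | 0.352 / 0.360 | 0.494 / 0.510 | 0.615 / 0.640 |
| 4 (5-day or slower) | 2.67 | 0.243 / 0.244 | 0.441 / 0.445 | 0.600 / 0.608 | 0.725 / 0.736 |
| 5 (review after Visit 3) | 3.33 | 0.294 / 0.295 | 0.518 / 0.522 | 0.685 / 0.691 | 0.804 / 0.813 |

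At r = 0.3 the gain is 18 to 19 points from three participants and about 8 from four. At r = 0.1 it is about 11 and 5 points. Block size hardly matters.

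**The case against.** The strongest reply is that the gate is not the only protection. The stopping rules apply to any participant at any time and need no DSMB meeting. If the 5th participant's Grade 2 event passes 96 hours, or her Visit 3 results show Grade 3, dosing halts whether or not the gate has opened. A clinically serious sign or symptom also stops enrolment at all sites until the medical monitor or sponsor gives permission. The board may decline to recommend, and escalation waits for the 4-week review. All of this stands. These protections act once a result exists, however, whereas the gate is meant to come before further exposure, and the 4-week review follows dosing of the last four.

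The size can also be challenged. Three-day spacing is a minimum, not a plan, and the SAP introduction attributes the earlier OAB trial's missing top dose to slow enrolment (protocol 1.4.2 cites finances). The slower-pace row may therefore be the realistic one. The 30% risk is an assumption, and the prior data summarized in the protocol suggest few laboratory changes. Some abnormalities counted here would also be too mild to alter the decision. These points reduce the gain but do not remove it.

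A reader might infer that stopping rule 2 is disabled for the 5th participant. It is not. It can rarely fire before the trigger (gross hematuria reported by telephone is one exception), but it remains active afterwards. A reader might also infer a blinded board, because 5.2.2 calls the 4-week review unblinded and the text on this review does not. Section 11.3 omits the word even for that 4-week review, so its absence shows nothing.

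**Conclusion.** The timing gap is certain for the 5th participant: the text permits a review at Day 3, her first post-dose safety laboratory tests are scheduled for Day 8 to 10, and nothing links the two. It extends to the 4th participant only at the fastest pace. The consequence is limited to release of four women, on average 2.7 active, within a cohort over about a week. At an assumed 30% risk the review's chance of seeing at least one case would rise from about 50% or 60%, depending on pace, to about 69%. These figures rest on the assumed risk and on abnormalities being visible by Visit 3.

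It would be too strong to say that participants are unprotected, or that the board will in fact meet on Day 3; the wording sets the earliest date only. Waiting for Visit 3 would not catch late events either, such as those at 13 to 76 days in the earlier OAB trial. This is an inexpensive safety improvement worth making, above all for 24,000 µg. It is not a defect that undermines the trial.

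**What to change.** In protocol 3.1, 5.3 (Dose Selection and Administration) and 11.3, and in SAP 4.1, time this review in each cohort to the availability of the 5th participant's Visit 3 laboratory results. Section 11.3 currently names only the first cohort for this review and should name both.

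Cost: 8 − 3 = 5 to 10 − 3 = 7 days per cohort, or 10 to 14 days over both, plus laboratory turnaround. It needs no extra participants, visits, samples or meetings.

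Separately, as a consistency correction unrelated to the timing: protocol 3.1 says "Enrollment of the first 5 participants in each cohort will be managed directly by the sponsor", and SAP 4.1 agrees, but 5.3 (Dose Selection and Administration) says four, and stopping rule 3 applies "in any of the first four participants of each cohort unless permission is given by the medical monitor". Align both with five.
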